Randomization will occur at the family level rather than the individual level. Prior to randomization, consented participants will be grouped according to family unit to prevent two diabetics in the same family being randomly assigned to different groups, creating cross-contamination. Once an entire cohort is recruited and assigned a family identification number, each number (family) will be randomly assigned to a study arm. Randomization will be conducted utilizing the Excel random number generation function. Randomization will be conducted by an investigator who will have no interactions with potential participants and has no supervisory role with program staff responsible for recruitment consent, or intervention delivery. Designated study staff will send the investigator a list of consented participants prior to the start of each new DSME cycle. The investigator will deliver the study arm assignments to a designated study staff member at the project site. Participants will be notified of their group assignment at least one week prior to commencement of study activities.

**Study arms description.** The standard care group will receive traditional DSME in a group format. However, those in the standard group will attend classes with other unrelated participants, unless two or more diabetics within the same family get assigned to the control group. The intervention group will receive the adapted Family Model of DSME in a family format, as described above. Participants in the Family Model will be encouraged to invite one to ten family members to participate in the DSME sessions as well as all other study events.

**Intervention:** Both the Family Model and the traditional DSME will include 10 hours of content comprised of 8 modules. The classes will be delivered over a 6-10 week period and each class will be approximately 75 minutes in length. To ensure fidelity, the DSME programs in both study groups will be facilitated by a Certified Diabetes Educator (CDE) or other licensed healthcare professional with expertise in the content areas. A translator/interpreter fluent in both English and Marshallese will be present for every

Title: *Family Model of DSME in the Marshallese Community*

PI: *[name]*

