## **Data Analysis**

### Sample size and power considerations

All of the power and sample size calculations and estimations were performed using PASS 2008 (NCSS, LLC. Kaysville, Utah. [www.ncss.com](http://www.ncss.com)). Our study design is a randomized two-group construct with 4 repeated time points (baseline, post intervention, 6 months, and 12 months). So at its core, the study is a two-factor design with repeated measures, which can be expanded into a general linear regression model, with main covariates being group assignment, time, their interaction, and adjustment for other covariates. The sample sizes will achieve 80% power to detect a medium effect of 0.3 in a design with 4 repeated measurements having a compound symmetry covariance structure. The correlation between observations on the same subject is assumed to be of moderate magnitude at 0.5, and the alpha level is 0.05. This hypothesized detectable effect is of the same magnitude as a study that reported approximately 0.5% change in HbA1c with the standard deviation of the change being 1.5%.

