#### Analysis of primary outcome

The primary outcome is change in HbA1c between baseline, post intervention, 6 months post-intervention, and 12 months post-intervention. Repeated measures of these outcomes will be obtained at four visits as described. Our primary analytic approach will use general linear models (GLM) and mixed models for continuous repeated measures to model the mean outcome differences and covariance structures between the groups. Using these models, group effects will be estimated and tested by comparing group-specific means at post intervention, 6 months, and 12 months, while conservatively adjusting for the baseline differences in ANCOVA like mixed regression models.

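### Control participants share group classes and families are the randomized unit, but the planned models allow only for within-person correlation; if outcomes correlate within class, the standard error of the HbA1c difference is understated

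*Combined protocol and SAP*

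**What the plan says.** Under Study Design and Procedures, the study arms description sets out two delivery formats. For the control arm, "The standard care group will receive traditional DSME in a group format", and "those in the standard group will attend classes with other unrelated participants". That sentence goes on to make an exception where two or more diabetic members of one family are allocated to control. For the other arm, "The intervention group will receive the adapted Family Model of DSME in a family format, as described above". On allocation, "Randomization will occur at the family level rather than the individual level".

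Both arms receive 10 hours of content in 8 modules over 6 to 10 weeks, led by an educator with an interpreter at every session. Sessions may be held at a clinic, a community centre or a place that the participant chooses.

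The sample-size section describes a regression model with "main covariates being group assignment, time, their interaction, and adjustment for other covariates". The only correlation it specifies is between observations on the same subject, set at 0.5. The primary analysis uses "general linear models (GLM) and mixed models for continuous repeated measures to model the mean outcome differences and covariance structures between the groups". Neither these sections nor those on secondary outcomes and missing data mention a random effect for class, family or cohort, a cluster-robust variance, or a design effect.

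**The concern.** Participants taught in the same class share a teacher, an interpreter, a timetable and each other's company. Their HbA1c results may therefore be more alike than those of participants in different classes. Where one arm is taught in groups and the other is not, or is grouped differently, the design is partially nested, and the grouping contributes variance to the treatment comparison.

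A model that allows only for repeated measures within a person treats classmates as independent. With a positive class ICC, it overstates the information in the control arm. The standard error of the primary difference is then too small, the confidence interval too narrow, and the false-positive rate above 5%.

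A family term is needed in its own right, because families are randomized and one family can contribute several diabetic participants. It would not solve the class problem, because it cannot absorb correlation between classmates from different families.

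**Working it through.** **The plan's own figure.** The sample-size section claims: "The sample sizes will achieve 80% power to detect a medium effect of 0.3 in a design with 4 repeated measurements". It states no N, so I take the total of 300 diabetics from the design section, 150 per arm, and a two-sided 5% test. The mean of four compound-symmetric measurements with correlation 0.5 has variance (1 + 3 × 0.5)/4 = 0.625. The standardized difference is then 0.3/√(0.625 × 2/150) = 3.286, and power is Φ(3.286 − 1.96) = 90.8%. The stated 80% is exceeded on this reading but not reproduced; 80% would need 110 per arm. The calculation contains no allowance for clustering. The point below does not depend on it.

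**Inputs for the class effect**
- Equal arms: design section (50/50).
- Class size m and class ICC: not in the documents, so assumed.
- Controls per cohort, relevant if each cohort has one control class: the design section gives six cohorts of 75, which is 450, but a total of 300. Half of 75 is about 37. Spreading 300 over six cohorts gives 50 per cohort and 25 controls.
- Family-arm design effect set to 1, to isolate the control classes. This is a simplification, not a statement about that arm.

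**Formulas**
- Control-arm design effect: DE = 1 + (m − 1) × ICC
- True SE divided by reported SE: R = √((1 + DE)/2)
- Actual type I error of a nominal 5% test: 2 × (1 − Φ(1.96/R))
- Power for effect 0.3: Φ(0.3/√(0.625 × (1 + DE)/150) − 1.96), once the SE is correct

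| m | ICC | DE | R | 1.96/R | Type I error | Power |
|---|---|---|---|---|---|---|
| any | 0 | 1.00 | 1.000 | 1.960 | 5.0% | 90.8% |
| 12 | 0.02 | 1.22 | 1.054 | 1.860 | 6.3% | 87.7% |
| 12 | 0.05 | 1.55 | 1.129 | 1.736 | 8.3% | 82.9% |
| 25 | 0.02 | 1.48 | 1.114 | 1.760 | 7.8% | 83.9% |
| 37 | 0.02 | 1.72 | 1.166 | 1.681 | 9.3% | 80.5% |

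Over a wider assumed range, the mildest corner (m = 5, ICC 0.01) gives R = 1.01 and 5.2%. The most severe (m = 37, ICC 0.10) gives R = 1.67 and 24.2%.

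**Width of a corrected interval.** With J equal control classes and n = J × m participants per arm, a Satterthwaite approximation gives df = (1 + DE)² / (1/(n − 1) + DE²/(J − 1)). The corrected interval is wider than the uncorrected one by the factor R × t(0.975, df)/1.96. At ICC 0.02:
- 12 classes of 12: df 34.6, t = 2.031, factor 1.09.
- 6 classes of 25: df 13.8, t = 2.147, factor 1.22.
- 6 classes of 37: df 12.4, t = 2.171, factor 1.29.
- 4 classes of 37 (about 300 in total at 75 per cohort): df 7.4, t = 2.336, factor 1.39.

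**The case against.** The documents do not show that classmates' outcomes are correlated. They give no ICC, class size or number of classes, and do not say whether class membership stays fixed across the 8 modules. A reader might infer that the standard errors are certainly too small. The text does not support that: the direction needs a positive ICC, and small classes with a low ICC make the effect negligible.

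Three other strong readings also fail.
- **Control classmates are always unrelated.** The protocol's exception for same-family controls says otherwise, and related controls are to be expected when whole families are randomized. The family term matters in the control arm too.
- **The Family arm is taught one family at a time, so only controls are clustered.** The text says only that the format is a family one. Sessions may be held at shared sites, and educators and interpreters serve both arms. Several families may share a session. In that case clustering exists in both arms and the table above is incomplete.
- **Each cohort has 37 controls.** The design section supports either 37 or 25, and the milestones table shows 22 controls in year one under the 70/30 split since replaced.

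It can also be said that clustering by family is the more basic omission, since it follows directly from the unit of randomization, and that a mixed model leaves room for further random effects. Both are fair. But room for a term is not a plan to fit it, and a family term alone leaves the correlation among unrelated classmates untouched. These objections limit the size and the wording. The omission stands.

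**Conclusion.** The point holds conditionally. Followed as written, the plan takes no account of shared control classes or of family, the unit of randomization. If the class ICC is positive, the standard error of the primary HbA1c difference is understated and the type I error exceeds 5%.

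The excess cannot be fixed from the documents. With clustering in the control arm only and equal arms, ICCs of 0.02 to 0.05 and classes of 12, or one class per cohort at ICC 0.02, put the true error rate at roughly 6% to 9%. These rates use a normal reference, which is optimistic when classes are few. At ICC 0 there is no excess from class. The change should be made, because it is specific and a class identifier not recorded during delivery may be impossible to recover later.

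**What to change.** 1. Record a class or session-group identifier for each participant with diabetes, in both arms, and state how many control classes run per cohort and whether families share sessions.
2. In the primary mixed model, prespecify a family random intercept in both arms and a class random intercept in the control arm, alongside the repeated-measures covariance. Add a class intercept in the Family arm if several families share sessions.
3. Use Kenward-Roger or similar small-sample degrees of freedom.
4. Keep the class term even if its variance is estimated as zero. An estimate of zero from a handful of classes is weak evidence that there is no class effect.
5. Reconcile the number of cohorts, the cohort size and the total of 300, because the number of classes and the power both depend on them.

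The cost is one more data field, one or two more model terms and a wider interval. At ICC 0.02 the widening is modest with many small classes (about 9% for 12 classes of 12) but about 22% to 39% with one class per cohort, for four to six classes of 25 to 37. In that case, splitting controls into more, smaller classes would recover precision, if delivery allows it.

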#### **Biometric Data**

The primary study outcome will be glycemic control as measured by HbA1c. Secondary biometric measures include: fasting glucose, waist and hip circumference, weight, height, BMI, blood pressure, and fasting lipids: total cholesterol, LDL, HDL, and triglycerides. HbA1c, fasting glucose, and fasting lipids will be collected via finger prick, measured using portable equipment, and immediately discarded after results are recorded. The biometric collection will be completed by qualified, trained research staff. A translator/interpreter will be present for each biometric collection.

#### **Survey Data**

We have developed a survey instrument that includes modules from the Diabetes Care Profile (DCP), the Behavioral Risk Factor Surveillance Survey (BRFSS), and internally developed modules pertaining to diet and physical activity. We will also collect demographics, contact information, and a medication inventory using study specific forms. The documents will be translated into Marshallese and field tested by the study's Marshallese Community Advisory Board. These surveys/forms will be administered at the pre-intervention data collection events and all post- intervention data collection events. All surveys will be either self-administered or interviewer-administered, depending on the preference and/or literacy of the participant. A Marshallese translator/interpreter will be present for all DSME sessions and data collection events.

Title: *Family Model of DSME in the Marshallese Community*

PI: *[name]*

**Table 1. Data Collection and Survey Instrument Description**

Biometric Measures	Biometric measures will include: HbA1c, fasting glucose, waist and hip circumference, weight, height, blood pressure, and fasting lipids: total cholesterol, LDL, HDL, triglycerides. Standardized protocols will be utilized for biometric measures. Waist and hip circumference will be measured to the nearest quarter inch utilizing a standard measuring tape. Waist to hip ratio will be calculated. Weight will be measured without shoes on a digital scale. Height will be measured without shoes to the nearest quarter inch. BMI will be calculated using weight and height measurements. Systolic and diastolic blood pressure will be measured with participant seated and arm elevated using a Sphygmomanometer and stethoscope or digital blood pressure monitor. Participants will be asked to fast for 8 hours prior to data collection. Point of Care tests will be used to test HbA1c, fasting glucose, and fasting lipids: total cholesterol, LDL, HDL, and triglycerides. Through a finger prick blood collection, we will test: 1) HbA1c using a Siemens DCA Vantage Analyzer. 2) Fasting glucose using the Cholestech LDX, 3) Fasting lipids using a commercial lipid panel kit and Cholestech LDX.
PCORI DSME Survey Instrument	A 43 item questionnaire that contains a total of seven modules: demographics, health status, health behavior, BRFSS diabetes, understanding, support, and health care access.
Participant Contact Form	This form is completed at consent to collect all relevant contact and address information as well as contact permissions, in order to schedule and administer study activities. Form will be updated as necessary.
Medication Inventory	A list of current diabetes medications will be collected at each data collection event so that we can control for variations in medications during the analytical phase and be better able to attribute changes in glycemic control to the DSME rather than confounding factors.

Title: *Family Model of DSME in the Marshallese Community*

PI: *[name]*

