#### Analysis of secondary outcomes

Analytic strategies similar to those used to evaluate our primary outcome will be employed to examine the proposed secondary measures. We will examine group effects, time effects and the interaction between them on other measures (fasting glucose, % weight loss, BMI, waist-hip ratio, lipids, and survey instrument data) using mixed and general/generalized linear ANCOVA like mixed models or general estimating equations (GEE), depending on the measurement scale of the outcome. Additional analyses would expand the existing multivariate models to include several other covariates for adjustments as well as to examine their associations with the outcomes.

Demographics and socioeconomic factors will be included for conservative adjustment if not comparable between conditions.

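### Blood pressure arm position and device are not pinned down, BMI change carries avoidable height error, and the list of analysed secondary outcomes does not match the list of secondary measures

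*Combined protocol and SAP*

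**What the plan says.** Three parts of the combined protocol and SAP bear on this point.

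- **Biometric Data** sets out the secondary measures: "Secondary biometric measures include: fasting glucose, waist and hip circumference, weight, height, BMI, blood pressure, and fasting lipids: total cholesterol, LDL, HDL, and triglycerides". It adds that "The biometric collection will be completed by qualified, trained research staff".
- **Table 1, Biometric Measures row**, gives the only blood pressure procedure in the document: "Systolic and diastolic blood pressure will be measured with participant seated and arm elevated using a Sphygmomanometer and stethoscope or digital blood pressure monitor". The same row promises that "Standardized protocols will be utilized for biometric measures". Height is listed there among the biometric measures and is read to the nearest quarter inch; then "BMI will be calculated using weight and height measurements". Study Design and Procedures has biometric data collected at four times: before and after the intervention, and 6 and 12 months after it.
- **Analysis of secondary outcomes** opens generally: "Analytic strategies similar to those used to evaluate our primary outcome will be employed to examine the proposed secondary measures". Its next sentence lists, in brackets, the measures to be examined for group, time and interaction effects: "fasting glucose, % weight loss, BMI, waist-hip ratio, lipids, and survey instrument data".

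**The concern.** There are three related weaknesses in how the secondary biometric measures are taken and analysed.

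1. **Blood pressure procedure.** The word *elevated* has no reference level. Staff could raise the participant's arm above the heart, or only lift it from the lap to heart level. A manual or a digital device may be used, and nothing keeps a participant on one type across four visits. At stake are the validity of reported levels and the comparability of readings between staff, sites and visits.
2. **BMI.** Adult height is effectively fixed. If each visit's BMI uses that visit's height, measurement error in height appears as change in BMI.
3. **Outcome lists.** Blood pressure is a named secondary measure but is missing from the itemised analysis list. Waist circumference survives only within the waist-hip ratio. A reader cannot tell whether a group effect on either is prespecified, so reporting it or leaving it out could each be defended after the data are seen.

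**Working it through.** The plan gives no SD, effect size or power for blood pressure or BMI, so there is no stated figure to reproduce. Inputs marked *assumed* are not in the documents.

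**Step 1. Cuff height.** A blood column of 1 cm (10 mm), with assumed densities of 1.055 for blood and 13.595 for mercury, gives 10 × 1.055 / 13.595 = 0.776 mmHg per cm. For assumed cuff positions of 5, 10 and 15 cm above the heart, readings are low by 3.9, 7.8 and 11.6 mmHg. At heart level the error is zero.

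**Step 2. Effect on the group comparison.** Take illustrative group means of 130 and 135 mmHg and subtract a common offset *o*: (130 − *o*) − (135 − *o*) = −5 for *o* = 0, 4 or 8. A constant offset leaves the group difference unchanged.

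**Step 3. Device mixing unrelated to study group.** With a fixed offset *d* between devices and a 50/50 mix, the added variance is *d*²/4. Assume a systolic SD of 15 to 20 mmHg, *d* of 3 to 10 mmHg, 150 per group (half of the stated 300), two-sided alpha 0.05, 80% power and no clustering. The minimum detectable difference is (1.960 + 0.842) × SD × √(2/150).

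| Assumed SD | No mixing | *d* = 3 | *d* = 10 |
|---|---|---|---|
| 15 | 4.85 | 4.88 | 5.11 |
| 20 | 6.47 | 6.49 | 6.67 |

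Variance rises by between 0.6% (9/4 over 400) and 11% (25 over 225). The loss is small.

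**Step 4. Device use that differs between groups.** The bias is the difference in device share times the offset: 0.1 × 3 = 0.3 mmHg up to 0.5 × 10 = 5.0 mmHg. If the share instead drifts between visits equally in both groups, the same shift falls on change over time and not on the group difference.

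**Step 5. Height error in BMI change.** BMI is weight over height squared, so an error *e* in height *H* shifts BMI by about BMI × 2*e*/*H*. With independent errors at two visits, the added SD of change is BMI × 2 × SD(*e*)/*H* × √2. With *H* = 62 in and BMI = 33 (both assumed), this is 33 × 2/62 × 1.414 = 1.505 kg/m2 per inch of error SD.

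| Source of height error | SD(*e*), in | Added SD of change, kg/m2 |
|---|---|---|
| Rounding to a quarter inch, 0.25/√12 | 0.072 | 0.11 |
| Assumed | 0.25 | 0.38 |
| Assumed | 0.5 | 0.75 |

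If one baseline height is used throughout, its error only rescales the change, by 2*e*/*H*. For *e* = 0.5 in that is 1/62, or 1.6% of the change.

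**Step 6. The two lists side by side.**

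| Secondary measure (Biometric Data) | In the itemised analysis list? |
|---|---|
| Fasting glucose | Yes |
| Weight | Yes, as percentage loss |
| BMI | Yes |
| Lipids | Yes |
| Waist and hip circumference | Only as their ratio |
| Blood pressure | No |

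The ratio is no substitute for waist itself: if both circumferences fall by 5%, then 0.95W/0.95H = W/H and the ratio does not move.

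**The case against.** A reader might infer that the trial's blood pressure readings are biased low, are noisy, and will go untested. The documents support none of these as stated.

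- **Biased low.** For a seated person, *elevated* may mean lifted to heart level. No cuff height is given, and the plan promises standardised procedures and trained staff. Even a real common offset leaves the group contrast intact (step 2). This objection stands: the finding is ambiguity, with bias only if the cuff is above the heart. The general promise does not remove the ambiguity, because no other blood pressure procedure is given.
- **Noisy.** The text allows two device types but does not say that they are swapped within a person. Random mixing costs little (step 3), and nothing in the documents shows that device use differs by group. This also stands. What remains is that no rule prevents such a difference.
- **Untested.** The opening sentence of Analysis of secondary outcomes covers the proposed secondary measures generally, and nothing excludes blood pressure or waist. This stands too: the analysis is inconsistently itemised, not absent.
- **BMI.** The plan does not say which visit's height enters BMI. Only the rounding component (0.11) rests on a documented precision, and even that uses an assumed height and BMI. Percentage weight loss is listed and is free of height error. These are fair limits on the size of the point. Still, height is among the biometrics collected at each event, nothing carries the baseline value forward, and the remedy is free.

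**Conclusion.** The point holds as a minor one, in three parts.

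- The blood pressure instruction is ambiguous on arm position and leaves the device open. A cuff above the heart would lower readings by about 0.78 mmHg per cm. Because a common shift cancels between groups, the exposure is mainly in reported levels and in consistency between staff and visits. A biased group difference, 0.3 to 5.0 mmHg in the illustration, would need device use to differ by group, which the documents do not indicate.
- If height is re-measured and used at each visit, BMI change carries an added SD of 0.11 kg/m2 from rounding alone, and 0.38 to 0.75 under the assumed error SDs. The resulting loss of power cannot be computed, since the plan gives no SD for BMI change.
- Biometric Data and the itemised list under Analysis of secondary outcomes disagree on blood pressure and waist circumference.

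The HbA1c primary analysis and the sample size are unaffected.

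**What to change.** 1. **BMI (Table 1).** State that BMI at every visit is computed from the baseline height. This costs nothing and can be applied retrospectively to data already collected.
2. **Blood pressure (Table 1).** State that the participant is seated with the arm supported at heart level. Keep one device type per participant across visits or, failing that, record the type at each visit. The cost is a line of text and brief staff instruction. If earlier readings were taken with the arm above heart level, their levels will not be comparable with later ones, so begin with a new cohort or record the method used.
3. **Analysis of secondary outcomes.** Add systolic and diastolic blood pressure and waist circumference to the itemised list so that it matches Biometric Data. The cost is three more outcomes in models already planned.

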### **Study Design and Procedures**

We will conduct a comparative effectiveness evaluation using a randomized control trial design of the adapted Family Model of DSME, and compare results of the Family Model of DSME with traditional DSME within the Marshallese population. The family model will cover the same concepts as the traditional format. However, the family model will incorporate culturally-adapted education and recommendations aimed at engaging family members in the management of the primary participant's diabetes, and family members will be invited to fully participate in the study. By contrast, the traditional model provides diabetes self- management education to the diabetic participant only, and the participant's family members do not participate in the classes or any other part of the

Title: *Family Model of DSME in the Marshallese Community*

PI: *[name]*

study. Biometric and survey data will be collected pre-intervention, post-intervention, 6 months post-intervention, and 12 months post-intervention. In the event missing data is identified, participants will be contacted to collect the missing data. A qualitative debriefing session will be held for each family between the final DSME session and the 6 month post-intervention to obtain qualitative data regarding the participant's perceptions of the intervention and implementation process. Participants will be offered a \$20 gift card as compensation for their time for each biometric data collection event and the qualitative debriefing session.

**Randomized participant assignment.** Six cohorts will be recruited, approximately three months apart. Each cohort will be comprised of 75 participants with diabetes, with 50% being assigned to the Family Model arm and 50% being assigned to the traditional DSME control group. The study sample size will be the total of each cohort; thus a total of 300 diabetics and up to 2000 family members (only those in the family model arm will be inviting family members). We initially chose an unequal group design (70/30), but after assessing Cycle 1 attrition, we needed to adjust the ratio in order to have sufficient control group numbers for analysis. Discussion with stakeholders resulted in support for this modification. Each participant will be randomly assigned to a group after consent.

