session. The family model intervention will be co-facilitated by a Certified Diabetes Educator or other licensed healthcare professional and a Marshallese staff person fluent in both English and Marshallese. The core elements of DSME intervention are: healthy eating, being active, monitoring, understanding blood glucose and taking medication, problem solving, reducing risks and healthy coping, mitigating complications of diabetes, and goal setting. These core elements will be maintained across both groups and are consistent with the American Association of Diabetes Educators' AADE seven self-care behaviors. Sessions will be provided at the Springdale AHEC clinic, the Jones Center, or at a location of the participant's choice.

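### The primary HbA1c model names neither cohort nor the randomised family, although families are randomised cohort by cohort and the ratio changed after Cycle 1

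*Combined protocol and SAP*

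**What the plan says.** **Randomisation.** Under Study Design and Procedures, "Randomization will occur at the family level rather than the individual level". Allocation takes place once a whole cohort has been recruited. On the ratio, the same section says "We initially chose an unequal group design (70/30), but after assessing Cycle 1 attrition, we needed to adjust the ratio"; the current text assigns half of each cohort to each arm. It plans six cohorts of 75, about three months apart, and a total of 300.

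**Primary model.** Analysis of primary outcome compares arm means at the three post-baseline visits, "while conservatively adjusting for the baseline differences in ANCOVA like mixed regression models". The power section describes the model "with main covariates being group assignment, time, their interaction, and adjustment for other covariates". Neither these sections nor Analysis of secondary outcomes nor Missing data mentions cohort, cycle or family.

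**Covariates.** The Medication Inventory row of Table 1 says "A list of current diabetes medications will be collected at each data collection event so that we can control for variations in medications", in order to "be better able to attribute changes in glycemic control to the DSME rather than confounding factors". Analysis of secondary outcomes allows additional models with further covariates and adds: "Demographics and socioeconomic factors will be included for conservative adjustment if not comparable between conditions". Missing data commits the HbA1c analysis to intent-to-treat.

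**The concern.** When the allocation ratio differs between cohorts, a pooled comparison without a cohort term gives Cycle 1 more weight in one arm than in the other. Any difference in HbA1c change between Cycle 1 and the later cohorts then enters the arm effect. Adjusting for each participant's baseline HbA1c removes only the part of that difference carried by baseline.

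Families are the randomised units, and the plan expects some to contain more than one participant with diabetes. Treating relatives as independent understates the standard error.

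The medication wording raises a smaller question. Medication recorded once the intervention has started may itself be a result of the arm or of earlier HbA1c. The curriculum covers "understanding blood glucose and taking medication" in both arms, and the arms differ in how far the family is engaged in managing the disease. A model that adjusts for later medication would not estimate the full effect of assignment.

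**Working it through.** **Inputs from the plan.** Six cohorts, 75 per cohort, total 300, and 70/30 changed to 50/50 after Cycle 1 (Randomized participant assignment). About 53 family-arm and 22 control completers in Year 1, and 110 and 50 in Year 2 (Table 2). Target 0.5 HbA1c point, SD of change 1.5, alpha 0.05 (Sample size and power considerations).

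**Assumed.** 53:22 stands for the numbers randomised in Cycle 1 (35:15 if cohorts hold 50). Later cohorts ran at 50/50. Tests are two-sided. The residual cohort difference δ, after baseline adjustment, is 0.25 or 0.5 point. Because 6 × 75 = 450 and not 300, several layouts are shown.

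**The plan's own figure.** The power section states 80% for an effect of 0.3 but names no N. With N = 300 split equally and the mean of four visits (variance factor (1 + 3 × 0.5)/4 = 0.625), I get 90.8%; for a single visit, 73.8%. The 80% is therefore not reproduced, but nothing below depends on it.

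**Step 1: gap in Cycle 1 share.** Gap = f1/F − c1/C, where f1 and c1 are the Cycle 1 counts and F and C the arm totals.
- Four cohorts of 75: 53/165.5 − 22/134.5 = 0.320 − 0.164 = 0.157
- Six of 75: 53/240.5 − 22/209.5 = 0.220 − 0.105 = 0.115
- Six of 50: 35/160 − 15/140 = 0.219 − 0.107 = 0.112
- Table 2 ratios throughout: 53/163 − 22/72 = 0.325 − 0.306 = 0.020

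**Step 2: bias and type I error.** Bias b = gap × δ. SE = 1.5 × √(1/F + 1/C). Type I error = 1 − Φ(1.96 − b/SE) + Φ(−1.96 − b/SE), for one visit and independent participants.

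**Step 3: variance cost of a cohort term.** Ratio = [FC/(F + C)] / Σ[fc/(f + c)], summed over cohorts. For example, 74.20/71.80 for four of 75 and 74.67/73.00 for six of 50.

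| Layout | SE | Bias, δ = 0.25 / 0.5 | Type I error, δ = 0.25 / 0.5 | Variance ratio |
|---|---|---|---|---|
| Six of 50 | 0.174 | 0.028 / 0.056 | 5.3% / 6.2% | 1.023 |
| Six of 75 | 0.142 | 0.029 / 0.058 | 5.5% / 6.9% | 1.024 |
| Four of 75 | 0.174 | 0.039 / 0.078 | 5.6% / 7.3% | 1.033 |
| Table 2 ratios | 0.212 | 0.005 / 0.010 | 5.0% / 5.0% | 1.000 |

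At δ = 0 the bias is zero and type I error is 5% in every layout.

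**Step 4: family, illustration only.** With m primary participants per family, variance is inflated by 1 + (m − 1) × ICC. Assume m = 2: the factor is 1.1 at ICC 0.1 and 1.3 at ICC 0.3. A test that ignores this has type I error 2 × [1 − Φ(1.96/√1.1)] = 6.2%, or 2 × [1 − Φ(1.96/√1.3)] = 8.6%, with no cohort drift at all. The documents give neither m nor the ICC.

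**Step 5: medication, illustration only.** The shift from adjusting is roughly the between-arm difference in medication change times its HbA1c effect. Assumed values give 0.05 × 0.5 = 0.025 to 0.10 × 1.0 = 0.10 point, in either direction, and zero if the arms do not differ. No input here comes from the documents.

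**The case against.** **On cohort.** The sizes rest on assumed drift, and 0.5 point of drift after baseline adjustment would equal the whole target effect. Cohorts are only about three months apart, and Table 2 keeps roughly 70/30 in Year 2, which leaves almost no gap. This is fair. A reader might infer that the comparison is biased; the documents do not support that, because they report no drift. They support only that the design permits the bias and the named model does not guard against it. Nor do they exclude a cohort term: the power section's unnamed covariates could hold one, but nothing commits to it.

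**On family.** Larger error rates appear when cohort and family effects are combined, but they should not be credited to cohort. In a simulation with two participants per family and ICC 0.3, omitting both terms gave 8.5% without drift and 10.4% with drift of 0.5. Most of the excess over 5% is clustering.

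**On medication.** A reader might infer that the primary model will adjust for follow-up medication. The documents do not say so. Table 1 explains why a form is collected, Analysis of primary outcome names baseline adjustment only, and the additional models under secondary outcomes are a natural home for medication. What stands is an ambiguity.

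**On timing.** One might assume that the first visit precedes randomisation and bar every post-randomisation variable. The text makes that unsafe. Participants and family member measures provides for people already randomised to the family arm when the initial HbA1c is read. Allocation is made from a list of consented participants, who are told their arm at least a week before study activities start. A strict ban could exclude baseline HbA1c itself.

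**Conclusion.** The point holds as a gap in the specification of the primary model. Cohort and family both belong to the randomisation scheme, and neither is named in the analysis.

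If later cohorts ran at 50/50 and 53:22 approximates Cycle 1, bias with six cohorts is about 0.03 to 0.06 HbA1c point for drift of 0.25 to 0.5, or roughly 6-12% of the 0.5 target. Type I error is about 5.3% to 6.9%. With four cohorts of 75 the upper figures are 0.08 point and about 7.3%. Under Table 2's ratios the effect is negligible. These error rates are for a single visit, not the planned repeated-measures model.

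The family part holds wherever a family contributes more than one primary participant; its size cannot be fixed from the documents. The medication part is secondary: the plan should say which medication values, if any, may enter the primary model, since adjusting for later values would depart from the effect of assignment that intent-to-treat promises. This should be settled before analysis, but it does not show that the result will be wrong.

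**What to change.** In Analysis of primary outcome, state the model as group, time, group × time, pre-intervention HbA1c and cohort as a fixed effect. Keep the repeated-measures covariance, and add a random effect or cluster-robust errors for the randomised family.

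Allow medication in that model only as its pre-intervention value, and label any model adjusting for later medication as exploratory. Bring Table 1, the power section and Analysis of secondary outcomes into line. State whether the pre-intervention data collection comes before or after allocation, and record which cohorts ran at which ratio.

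The cost is wording: cohort, family number and medication at each visit are already recorded. The cohort term raises variance by about 2-3%. For 0.5 point with SD 1.5 at one visit and N = 300, power (noncentral t) falls from 81.9% to 81.0% with six cohorts of 50, or from 81.7% to 80.4% with four of 75. For an effect of 0.3 averaged over four visits in the four-cohort layout, it falls from 90.5% to 89.5% (normal approximation). Accounting for family may lower power further, but that loss comes from randomising families and is present whether or not the model shows it.
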